days (a total of 2.1 L). Anthropomorphic measurements, plus fasting blood and urine analyses were made weekly. It was found that elevating blood β HB concentrations from 0.1 to 4.1 (±1.1) mM three times a day for 28 days had no effect on body weights or composition, fasting blood glucose, cholesterol, triglyceride or electrolyte concentrations, nor blood gases or kidney function, which were invariably normal ³⁶. In addition, a 28-day study in patients with type 2 diabetes also on 26.8 g t.i.d. po found that all participants had >90% adherence, defined as consumption of at least 76 of the maximum 84 KE drinks. Thus, the KE drink was well-tolerated. Adverse symptoms were self-recorded by participants following each of their drinks and were ranked as 'mild', 'moderate' or 'severe'. Overall occurrence of adverse symptoms is expressed relative to the total number, 1,588, of drinks consumed throughout the entire study; mild nausea (5/1,588 = 0.3%), mild headache (5/1,588 = 0.3%) and mild gastric discomfort (9/1,588 = 0.5%) were the only reported symptoms ³⁷. Mild nausea was reported following 6 of the 2,016 drinks consumed in the 28-day healthy control study ³⁶.

Research staff will administer the first dose of KE drink at Visit 3 in lab to monitor subjects (day 1), and then subjects will be sent home and asked to take a second dose of KE drink with their next meal (day 1). For days 2 through 7, participants will take 12.5g (25mL) TID, and on day 8, the dose will be increased to 25g (50mL) TID as tolerated. KE dose will be titrated down to a tolerated level if necessary. Participants will be asked to take the KE doses with meals to decrease side-effects of hypoglycemia. If participants are experiencing feelings of low glucose levels and/or a blood glucose reading of <65mg/dL (via unblinded continuous glucose monitor and/or KetoMojo reading), participants will be asked to skip the KE dose and wait until their next meal to take a dose. Glucose and ketone body levels will be monitored for the first ~7days using Keto-Mojo (optional) to decrease chances of hypoglycemia, as well as taken weekly for the duration of the KE intervention (optional). Glucose and ketone body levels will also be monitored prior to the post-intervention clinical testing and imaging. Staff will ask participants to limit their alcohol consumption to a maximum of one glass per day and take the final daily dose at least 4 hours prior to sleep.

Magnetic resonance imaging (MRI) will be performed on a 3 Tesla Philips Achieva system (Philips, Best, The Netherlands). A 3D inversion recovery-prepared turbo-field-echo was performed in the TR/TE/TI=9.8/4.6/1041ms; sagittal plane using turbo factor=200; single average; FOV=240x200x160mm; acquired Matrix = 240x200x160 slices and reconstructed to 1mm isotropic resolution. MR-spectroscopy and other sequences will also be performed. Resting-state fMRI scans will serve as a secondary outcome measure and be acquired using a 32-channel head coil and multiband sequence ⁵⁰, with nominal parameters: (TR/TE/FA = 720/34/52, 2mm isotropic resolution, 72 slices). Data are collected with eyes fixated on a cross for 10 minutes ⁵¹. Pre-processing follows our standard pipeline that includes physiologic noise reduction and thorough motion correction ^{52, 53}. Graph theory analysis will be used to identify the most highly connected nodes following published methods. Briefly, ROIs will be represented as nodes and pairwise correlations, based upon the mean time series for each ROI, will serve as weights over corresponding edges, thresholded by FDR correction, p<0.05 ^{52, 53}. Change from baseline will serve as the primary measure of interest. Magnetic resonance spectroscopy (MRS) may optionally complement the MRI sequence. MRS may be performed either at University Hospital or North Campus fMRI Laboratory.

PET imaging will be performed in 3D imaging mode on a Biograph 6 TruePoint PET/CT scanner (Siemens Molecular Imaging, Inc., Knoxville, TN), which acquire 63 transaxial slices (slice thickness: 2.4 mm) over a 15.2 cm axial field-of-view. Images were corrected for scatter and motion. The PET imaging frames will be spatially coregistered within subjects with a rigid-body transformation to reduce the effects of subject motion during the imaging session ⁵⁴. Statistical parametric mapping (SPM)

software (SPM12; Wellcome Trust Centre for Neuroimaging, University College, London, England [https://www.fil.ion.ucl.ac.uk/spm/software/spm12/] will be used for PET-MRI registration using the cropped T1-weighted MR volumetric scan. Freesurfer software (http://surfer.nmr.mgh.harvard.edu) will be used to define cortical and subcortical volumes-of-interest (VOI).

MRI-based PET partial volume correction: We will use the Müller-Gärtner partial volume correction technique, which is based on the assumption that white matter uptake is homogeneous and uses gray matter (GM), white matter (WM) and cerebrospinal fluid (CSF) to correct the partial volume effect in GM tissues ⁵⁵. Using the segmented images and the assumed PET resolution, the method calculates the spill-out from WM to GM and subsequently subtracts it from the GM. Similarly, it also calculates the spill-out from the GM to the surrounding tissues and compensates for the difference to the GM. The result is a grey matter image with corrected activity values in all voxels.

Statistical analysis

We will use a paired t-test to assess for changes in glucose metabolism before and after the KE supplementation. Glucose metabolic changes include 7-10 daily average and fasting glucose based on continuous glucose monitoring that can be complemented by cerebral FDG PET SUVr in the subset undergoing PET imaging.

As a *post hoc* and only exploratory analyses we will regress differences in with KE -induced changes of the various clinical and laboratory outcome measures.

Sample size estimation: This experiment is a first in human study of this drug for treatment of glucose changes in a neurodegenerative condition. Based on the 28-day t.i.d. KE intervention study performed in patients with type 2 diabetes mellitus ³⁷, and similar effect size in our cohort and using a power of 0.8 and a two-sided alpha of 0.05 for our primary analysis that will compare pre and post KE, we arrive at a total sample size of 30.

Scientific rigor: All tests and neuroimaging procedures used in this proposal have been validated and protocols have been published. Both PET and MR neuroimaging assessments will follow established and published acquisition protocols. Neuroimaging analysis will include well-validated and widely used software packages and processing pipelines such as SPM12, FreeSurfer, FSL, and AFNI. All equipment for mobility testing is commercially available and vendor-provided (validated) outcome parameters will be used. The neuropsychological test battery includes tailored components for use in PwPD ⁵⁶. We will rigorously guard against Type I and Type II errors and correct all our statistical inferences with family-wise error and false discovery rate corrections where appropriate. This reproducible and rigorous methodological and analysis approach will ensure results and conclusions that can be replicated by other investigations.

Pitfalls, problems, and alternative strategies

Ineligibility and attrition rate:

Protection of Human Subjects

i) Human Subjects Description of subject populations:

- Healthy control persons, M/F, age 45 years and over without a history of neurological or psychiatric disease or significant GI disease or uncontrolled medical comorbidity will be recruited (net n=4).
- ii) PD (net n=16) Diagnosis of PD in PD participants (M/F, age 45 years and over) will be based on the United Kingdom Parkinson's Disease Society Brain Bank Diagnostic Research Criteria (patients with clinically significant dementia will be excluded from PD subset and may participate in LBD/PDD subset (i.e., fails informed assent screening criteria and has significant evidence of iADL functions, such as ability to take own medications while administering the pre-consent screening questionnaire).
- iii) Persons diagnosed with Lewy Body Dementia (LBD) based on the Fourth consensus report of the DLB Consortium inclusion criteria for probable DLB or Parkinson's Disease Dementia (PDD) based on the criteria set by Emre *et al.* for PDD (M/F, age 45 years and over; net=10).

Exclusion criteria:

 Exclusion for all subjects: (a) Evidence of large vessel stroke or mass lesion on MRI; (b) Regular use of anti-cholinergic drugs or taking high dose (>100mg QD) of quetiapine (c) history of significant GI disease, (d) significant metabolic or uncontrolled medical comorbidity, (e) poorly controlled diabetes, (f) pregnancy or breast feeding, (g) suicidal ideation as determined by Beck Depression Inventory Question 9, (h) current excessive alcohol use as determined by investigator, and (I) subjects with contra-indications to MR imaging, including pacemakers, metal fragments in the body, or severe claustrophobia (for participants undergoing imaging); (i) participants with significant prior radiation exposure may not be eligible for the optional imaging portion of this study.

Recruitment: Subjects will be recruited from the University of Michigan Movement Disorder clinics, UM research studies website, Data Direct, and/or advertisement/flyers.

ii) Sources of Materials:

Information gathered specifically for this research project includes test results from clinical test scales, psychometric cognitive measures, neurobehavioral rating scales, clinical motor data, questionnaires, and data derived from PET and brain MRI.

iii) Potential Risks (as described in informed consent document):

Confidentiality of Research Information: The research data to be collected from subjects will consist of confidential information relating to clinical, motor, cognitive, neurobehavioral, and neuro-imaging functions. These research data are not intended for entry into the subjects' clinical medical records. However, the data remain potentially discoverable. This may lead to violation of privacy and embarrassment of the subject.

Clinical Testing: Risks regarding the clinical assessment are limited to fatigue, frustration and momentary embarrassment that may occur when one experiences difficulty performing a task or learning a new skill. There is an infrequent risk that the blood sample method may cause minor bruising at the injection site. There is a very rare risk for infection. There is a rare risk that you may feel dizzy, lightheaded, or faint after the blood draw. There is an infrequent risk of pain or infection associated with finger prick using Keto-Mojo.

Motor Testing: Many of the tests are comparable to normal standing and walking conditions that you may experience in everyday-life. Nonetheless, there is an infrequent risk of falling or near-falling during these tests which may result in fall-related injuries. There is a very rare risk that the sensors to measure overall movement and balance may become detached and that you may trip. You may also trip on the pressure sensitive mat.

Risks associated with clinical, neuropsychological and behavioral testing: This study involves cognitive tests and questionnaires. The cognitive tests are not harmful, but some people find them frustrating and concerning. Risks regarding the neuropsychological and behavioral assessment are limited to fatigue, frustration and momentary embarrassment that may occur when one experiences difficulty performing a task or learning a new skill. Some people may be uncomfortable/embarrassed disclosing personal information or become nervous about memory testing and may experience discomfort or become tired. Study team members are very well experienced in the assessment of older individuals and persons with dementia, understanding the need for breaks, gentle reassurance, or reinforcement. All assessments will be stopped if requested by the participant.

MRI scan: There is a substantial risk to persons who have metallic objects inside their bodies, as the magnet in the MR scanner can cause these to move. Consequently, participants with pacemakers or metallic objects located in the eye, ear, brain, or blood vessel walls will be excluded from the optional imaging portion. Participants who developed claustrophobic anxiety during scanning found that this fear dissipated within 15 min while remaining in the scanner, or as necessary, after exiting the scanner. There also is the potential that imaging could reveal a previously unrecognized but pre-existing abnormality. Many such abnormalities are not clinically significant, but they may cause anxiety or require further investigation by a personal physician. If one of the investigators identifies such an abnormality, they will contact the personal physician, who will arrange for appropriate care.

PET-CT scans & venipuncture: Insertion of a catheter for intravenous injection of the PET radiopharmaceutical may be commonly associated with slight pain or bruising at the puncture site and rare chance of infection. Participation in this research study will involve low level exposure to radiation associated with the PET, CT, and DEXA scans.

The use of [¹⁸F]FDG is considered to be generally safe and effective as approved by the University of Michigan Radioactive Drug Research Committee in accordance with Food and Drug Administration regulations (21 CFR 361.1). Certified staff will be in attendance at all times during the study. A physician will be available, and an emergency cart is located in the PET Facility for treatment of any adverse reactions that may occur.

During the course of this study, the participant will be exposed to radiation from the two [¹⁸F]FDG PET-CT and two DEXA scans. The risks associated with the amount of radiation exposure participants receive in this study are considered very rare and comparable to everyday radiation exposure risks.

The biological effect of radiation in humans is measured in terms of Sieverts (Sv) or mSv (1/1000 Sv), which is a unit of uniform whole body exposure. The radiation exposure a participant will receive from the CT, and [¹⁸F]FDG PET scan is equivalent to a uniform whole body dose of 12.3 mSv, which is approximately 24.6 % of the annual radiation exposure (50 mSv) permitted to radiation workers by federal regulations. The participant will be instructed to use the bathroom and urinate as soon as possible after the PET scans in order to minimize bladder exposure. The radiation the participant will

be exposed to from each DEXA scan is 0.0310 mSv, which is significantly less than 1% of the permitted annual radiation exposure.

There is no known minimum level of radiation exposure that is recognized as being totally free of the risk of causing genetic defects (cellular abnormalities) or cancer. However, the risk associated with the amount of radiation exposure that participants will receive from this study is considered to be low. The risk of a side effect from this level of radiation exposure is very rare. The risk from radiation exposure of this amount is considered to be similar to other everyday risks, such as driving a car.

No PET studies will be performed on pregnant, nursing, or potentially pregnant women.

A urine pregnancy test will be performed on all women of childbearing potential within 48 hours prior to the PET scanning session.

Risks associated with the ketone ester: The risks to participants are low. Studies in humans have shown evidence of nausea, gastro-intestinal discomfort, abdominal distention, diarrhea, dizziness, lightheadedness, sweating, headache, keto flu-like symptoms, heartburn, shakiness, sleep changes, other symptoms of hypoglycemia, and/or increased glucose levels. Poor or bitter taste is a more common side-effect. Therefore, the KE drink may be diluted. The KE in this study has received GRAS (Generally Regarded As Safe, GRN No.515) certification from the FDA ⁵⁷, is commercially available in the United States and prior work has shown that the 25g tid po dosing regimen proposed in this study has been found to be safe and generally well-tolerated in healthy controls and patients with type 2 diabetes mellitus ^{36, 37}. If side effects occur, the study team will decrease the dose and/or ask participants to skip a dose until their next meal.

Data Study Monitoring Plan (DSMP): [name] will act as the Data Safety Monitoring Plan members for this study. All adverse events and other study related events will be discussed at monthly investigator meetings. Adverse events will be classified according to standard criteria and reported to the IRBMED (relevant University of Michigan IRB) according to standard guidelines. Serious adverse events will be reported within 24 hours.

For risk of suicidality (if participants select answer responses 2 or 3 for question 9 on the Beck Depression Inventory, i.e. 'I would like to kill myself' (answer 2) or 'I would like to kill myself if I had a chance' (answer 3) then the staff will hand out the UM Depression brochure, refer to the contact information and inform [name] or [name] who will discuss this with the participant. The face-to-face or video conversation with the physicians will occur during that visit and will not be deferred. There will be a safety plan in place before the patient leaves the building.

References

1. [name] NI, Koeppe RA, Minoshima S, Giordani B, [name] RL, Frey KA, Kuhl DE. Cerebral glucose metabolic features of Parkinson disease and incident dementia: longitudinal study. J Nucl Med. 2011;52(6):848-55. Epub 2011/05/17. doi: jnumed.111.089946 [pii]

10.2967/jnumed.111.089946. PubMed PMID: 21571793.

- Aim 1 Analytic Approach: We will compare mean baseline serum BHB levels to mean BHB levels measured at the 60 minute assessment. We will use the Wilcoxon rank sum test (non-parametric equivalent of standard two sample t test) to evaluate our Aim 1 hypothesis. We will have values available at 2-hours and 4-hours as well to test the duration of the effect. We will also collect serum glucose values at each of the four time points (baseline, 1 hours, 2 hours, and 4 hours).

Aim 2: To evaluate the tolerability of the Modified Curtis Protocol in PD.

- **Hypothesis 2:** Participants will not experience worsening in Movement Disorder Society Unified Parkinson Disease Rating Scale part III (MDS-UPDRSIII) scores.
- Aim 2 Outcome Measure: Change from baseline to 1 hour in MDS-UPDRSIII scores.
- Aim 2 Analytic Approach: Similarly to Aim 1, we will compare baseline MDS-UPDRS_{III} scores to those obtained at the 60-minute assessment using the Wilcoxon rank sum test. Similar to Aim 1, we will also have values available at 2-hours and 4-hours as well to test the duration of the effect. We will collect additional clinical measures and measures of tolerability including timed up a go test (TUG), finger tapping test (FTT), mini Addenbrooke's Cognitive Examination (mini-ACE), gastrointestinal symptom rating scale (GSRS), and adverse event report.

Sample Size

For the purposes of calculating a sample size, we used parametric testing by means of a paired sample t-test. Please note that to reduce the risk of type 1 error due to outliers in our dataset, we propose to use analogous non-parametric testing in our final test of Aim 1. Based on previously studies looking at change in BHB after consumption of this ketone ester, we expect an increase in 0.5 mmol [4]. This would also be the minimum change needed to achieve ketosis. Using a two-side alpha of 0.05, a power of 0.80, and a proposed standard deviation of 0.5 mmol in BHB serum levels, a sample size of 10 participants will be sufficient to test our Aim 1 hypothesis.

Schedule of Activities

Evaluation	Screen and Informed Consent	In Person Study Visit	Telephone Follow Up Visit
Setting	In-Person/Phone	In-person	Phone
Discuss Study Overview	х		
Assess for Eligibility	Х		
Informed Consent	Х		
Modified Curtis Protocol		х	

MDS-UPDRSı, ıı, ıv (Baseline)	х	
MDS-UPDRSIII (Baseline, 1, 2, and 4 hours)	х	
Mini-ACE (Baseline, 2, and 4 hours)	х	
TUG (Baseline, 1, 2, and 4 hours)	х	
FTT (Baseline, 1, 2, and 4 hours)	х	
Serum ketones and glucose (Baseline, 1, 2, and 4 hours) via Keto Mojo Meter	х	
GSRS (Baseline, 1, 2, and 4 hours)	Х	x
Report of side effects (1, 2, and 4 hours)	Х	
Follow Up Report of Potential Side Effects		x

Participants screening and informed consent will occur per the original protocol document and be introduced as an optional sub-study. This will all occur in advance of the in-person study visit and prior to any clinical testing. The in-person study visit will occur in the lab of [name] at Domino Farms. This is the primary site for PD human subjects research visits in our UM Movement Disorders Neurology group. Participants will be asked to withhold their usual parkinsonian medications (dopaminergic medications or amantadine) the morning of the inperson study visit and are to bring them to the study visit in order to take them immediately after completion of the day's activities. This is requested in order to prevent a medication induced fluctuation in motor score from impacting the repeated MDS-UPDRS_{III} clinical assessments. They will also be required to arrive in the fasted state per the Modified Curtis Protocol. They will then undergo baseline testing including the MDS-UPDRS_{I-IV}, the Mini-ACE test, the TUG, the FTT, the GSRS, and blood testing. The order of these test may vary depending on the participant and visit context. This is collectively estimated to take 30-60 minutes from arrival.

The next hour will consist of the Modified Curtis Protocol at which time participants will first consume the fat and coffee supplement. Thirty minutes later, they will consume the KE. Fifteen minutes later they will begin 5 minutes of stretching in preparation for 10 minutes of low intensity exercise. The exercise component will be on a stationary bicycle and will be interval training type exercise but at low intensity given possible deconditioned state of participants. It will start with 2 minutes of cycling with minimal added resistance while increasing cadence from 30 to 60 rotations per minute (rpm). There will then be two cycles of 30 seconds of modestly increased resistance with a cadence of 80 rpm followed by 2.5 minutes of minimal resistance at a cadence of 70 rpm. This will be followed by a cool down still at minimal resistance decreasing cadence from 60 to 30 rpm.

Sixty minutes after consumption of KE, or 30 minutes after completion of the Modified Curtis Protocol, participants will undergo repeat testing including the MDS-UPDRS_{III}, TUG, FTT, GSRS, a side effect assessment, and serum glucose/ketone body lab testing via Keto-Mojo. This same testing plus the Mini-ACE will also recur after 120 minutes (2 hour) and 240 minutes (4 hour) from the time of time the KE drink was finished. After the 4-hour testing is complete,

participants will be allowed to take their held medications, can resume their normal diet, and will be dismissed for the day.

Our study team will follow up with participants by phone in the 48 hours following the in-person Study Visit to ask about potential side effects and to repeat the GSRS as well as ask the closing question which is a Likert scale survey question regarding likeliness that the participant feels they could repeat this protocol on a daily basis. Once the follow-up phone call ends, the sub-study will be complete.

Visit 3 in the original study document consists of psychiatric clinical testing as well as optional motor and cognitive testing. Participants who opt to take part in this sub-study will be exempt from completing the original planned assessments for this day as per the Schedule of Activities (SoA) (besides the Beck Depression Inventory II and Spielberger Trait Anxiety scale which will be completed by all participants at visit 3). The administration of the ketone product and blood lab testing for this visit would be per the sub-study protocol as opposed to the original protocol. Participants would still receive the sleep tracking ring, pregnancy testing (if applicable), and drug accountability before starting the original intervention protocol.

For individuals who cannot tolerate the Curtis protocol intervention, study staff will send home the participants without the KetoneAid supplement and call them within 48 hours to monitor any side effects from testing. Participants may be asked to come back in to the lab to take the KE supplement without any additional testing to assess tolerability of the ketone ester drink alone.

Modified Curtis Protocol Components:

Ketone Ester:

Please see original document for additional information regarding the exogenous ketone supplement by the brand KetoneAid (D- β -Hydroxybutyrate-(R)-1,3 Butanediol). There will be no change to the dose of D- β -Hydroxybutyrate-(R)-1,3 Butanediol which, per the original protocol, is a single 12.5 g dose.

Fat and Coffee Supplement:

The original protocol uses a combination of coffee, grass-fed butter and cream, and coconut oil. Coffee has been suggested to have multiple benefits in PD [6]. Coconut oil is a source of medium chain triglycerides which serve as precursors to ketone bodies. Lastly, grass fed dairy is a source of low carbohydrate and high fat calories which are lower in unsaturated fat. Ingredients for the chosen supplement include coconut oil powder, grass fed butter powder, instant organic coffee powder, medium chain triglyceride oil powder, natural coffee flavor, and real salt. The supplement is called Keto Coffee and made by the brand Fat Fuel. One serving is 234 calories and contains 120 mg of caffeine.

3. Enrollment Criteria

Inclusion criteria:

 Diagnosis of PD (M/F, age 45 years and over) will be based on the United Kingdom Parkinson's Disease Society Brain Bank Diagnostic Research Criteria (patients with clinically significant dementia will be excluded, i.e., fails informed assent screening criteria and has significant evidence of difficulty with iADL functions, such as ability to take own medications while administering the pre-consent questionnaire).

 Persons diagnosed with Lewy Body Dementia (LBD) based on the Fourth consensus report of the Dementia with Lewy Body (DLB) Consortium inclusion criteria for probably DLB or Parkinson's Disease Dementia (PDD) based on the criteria set by Emre *et al.* for PDD (M/F, age 45 years and over)

Exclusion criteria:

- 1. All exclusion criteria from original protocol applies to sub-study
- 2. Significant metabolic or uncontrolled medical condition, including significant cardiovascular disease or significant musculoskeletal disorder which would make it unsafe to participate in cardiovascular exercise
- 3. Lactose intolerance

4. Potential Risks

Please see original document for risks associated with confidentiality of research information, clinical testing, motor testing, neuropsychological testing, and the ketone ester supplement.

Exercise:

Common risks of cardiovascular exercise include fatigue, general discomfort, temporary muscle soreness and pain. Infrequent risks include muscle strain and rare events include musculoskeletal injury or cardiovascular event. Risks to participants have been minimized by limiting the duration of exercise and by limiting participation of those with higher risk of these events through exclusion criteria. Moreover, participants will be guided through gentle stretching prior to initiating exercise to minimize the risk of injury. The HIIT intervals have been intentionally designed with a gentle level of intensity to ensure tolerability for PwP. HIIT is a type of cardiovascular exercise which was shown to have no difference in adverse events when compared to moderate intensity exercise in middle age and older adults with diabetes. [7]

Fat and Coffee Supplement:

Common risks with consumption of this coffee supplement primarily include possibility of poor taste and worsening of tremor. Infrequent side effects of caffeine include anxiety, palpitations, headaches, dizziness, and insomnia. Infrequent side effects of this supplement include stomach discomfort, nausea, bloating, and diarrhea. These risks are limited by limiting the participants to a single serving in the morning which consists of 120 mg of coffee which is equivalent to a standard cup of coffee.

5. Data Study Monitoring Plan:

[name] will act as the Data Safety Monitoring Plan members for this study. All adverse events and other study related events will be discussed at monthly investigator meetings. Adverse events will be classified according to standard criteria and reported to the IRBMED (relevant University of Michigan IRB) according to standard guidelines. Serious adverse events will be reported within 24 hours.

6. References

 Youle RJ. Mitochondria-Striking a balance between host and endosymbiont. Science. 2019;365(6454). Epub 2019/08/17. doi: 10.1126/science.aaw9855. PubMed PMID: 31416937.

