Milestone of recruitment success are net completion of 9 persons for year 1.

Table 1: Study enrollment &main assessments	NC	PD	PDD/LBD	TOTAL
Baseline clinical assessment with (optional) [¹⁸ F]FDG PET- CT & brain MRI	NC=4	PD=16	PDD/LBD=10	n=30

30-day (± 7 days) KE 25 g tid po intervention with pre/post clinical assessments)	NC=4	PD=16	PDD/LBD=10	n=30
Post-intervention clinical assessment with (optional) [¹⁸ F]FDG PET-CT & brain MRI	NC=4	PD=16	PDD/LBD=10	n=30
Total subject net recruitment	NC=4	PD=16	PDD/LBD=10	n=30*

aims

**Net* recruitment n=30; *gross* recruitment to account for attrition n=42. We will aim to complete 10 participants in the optional sub-study, all who will be recruited from the net recruitment pool.

Design: Exploratory open-label KE drink 25 g t.i.d. po (titrated up from 12.5g t.i.d) supplementation pilot study.

Methods: After screening for study eligibility and obtaining informed consent (including eConsent), study participants will undergo the baseline clinical (vital signs, respiration, and general neurological assessment and optional imaging protocol (separate days). For patients taking dopaminergic medication, the motor component of the test battery will be performed in the dopaminergic medication 'off' state in the morning after withholding their dopaminergic medications in the PD overnight, i.e., temporarily postponing the morning dose until the motor exam has completed. The remainder of the test battery will be performed in the remainder of the test battery will be performed in the medication 'on' state. Participants will also complete some testing in a fasted state. For participants who were not consented prior arriving for their baseline visit, study staff will obtain a waiver of consent during the screening call for fasting and withholding dopaminergic medications prior to their visit. Qualified personnel who have been trained in the use of the instruments and have undergone inter-rater reliability evaluations will perform the assessments.

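### Sub-study Aim 2 is tolerability, but its only stated outcome is a 1-hour motor score, and no outcome counts participants who cannot finish the regimen

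*Combined protocol and SAP*

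**What the plan says.** The Optional Sub-Study Protocol, section 2 (Study Design), gives Aim 2 as: "To evaluate the tolerability of the Modified Curtis Protocol in PD". The hypothesis is "Participants will not experience worsening in Movement Disorder Society Unified Parkinson Disease Rating Scale part III (MDS-UPDRSIII) scores", and the outcome is "Aim 2 Outcome Measure: Change from baseline to 1 hour in MDS-UPDRSIII scores". The analytic approach compares baseline with 60-minute MDS-UPDRS III scores by a Wilcoxon test, with 2-hour and 4-hour values available to examine duration.

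Other measures are listed under the same aim as additional. They include the timed up and go test, finger tapping, the mini-ACE and "gastrointestinal symptom rating scale (GSRS), and adverse event report". The Schedule of Activities places GSRS at baseline, 1, 2 and 4 hours and on the phone call, and side-effect reports at 1, 2 and 4 hours. The closing phone call also asks how likely the participant thinks it is that they could repeat the regimen daily.

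On people who do not tolerate the regimen, the text after the Schedule of Activities says: "For individuals who cannot tolerate the Curtis protocol intervention, study staff will send home the participants without the KetoneAid supplement". They are called within 48 hours about side effects and may be asked back to take KE alone, with no further testing.

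On numbers, the Table 1 footnote of the main protocol says "We will aim to complete 10 participants in the optional sub-study", and the Timetable paragraph likewise speaks of 10 recruited to complete. The sub-study's Sample Size paragraph justifies 10 for Aim 1 only.

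**The concern.** The question and the measure do not match. The plan recognises a group who cannot tolerate the regimen, but no stated outcome counts them. The risks the sub-study lists for the supplement include stomach discomfort, nausea, bloating and diarrhea, none of which MDS-UPDRS III measures. Worsening of tremor is also listed, so the motor score has some relevance, but it is not tolerability.

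At stake is the Aim 2 conclusion. An analysis of those with a 1-hour score could find no motor worsening and be reported under a tolerability aim without the reader learning how many people started and could not finish. The main protocol's Overview gives the goal of the sub-study as feasibility, so that number is what a follow-on study would need.

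**Working it through.** **1. The plan's own figure.** Inputs from the Sample Size paragraph: BHB difference 0.5 mmol, SD 0.5 mmol, two-sided alpha 0.05, power 0.80, paired t-test. The standardised difference is 0.5/0.5 = 1.0, taking the SD as that of within-person differences (the text does not say). Exact power from the noncentral t with noncentrality 1.0 × √n is 0.748 at n = 9 and 0.803 at n = 10. So 10 reproduces, but for BHB only. No figure in the documents supports Aim 2.

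**2. Who has a 1-hour score.** Set time 0 at the coffee/fat supplement. KE follows at 30 minutes. Stretching starts 15 minutes later (45), lasts 5 minutes (to 50), and cycling lasts 10 minutes (to 60). The test is at 90 minutes, which is 60 minutes after KE and 30 minutes after the regimen ends. By stopping point:

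- Stops after the supplement, before KE: neither reference time exists, so the 1-hour test is undefined.
- Takes KE but does not finish the exercise: the KE reference exists and the completion reference does not. A score is possible, but the plan does not say whether it is taken or used.
- Finishes the regimen but becomes unwell before 90 minutes: both references exist. Whether the person is tested before going home is not stated.

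The sub-study protocol states no Aim 2 analysis set and no rule for a missing 1-hour score.

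**3. What a completer-only comparison can show.** Among completers, the count who could not finish is 0 by definition. For x intolerant among n starters, the exact (Clopper-Pearson) 95% limits are the 0.025 quantile of Beta(x, n − x + 1) and the 0.975 quantile of Beta(x + 1, n − x). The counts below are assumptions, each adding x to 10 completers.

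| Intolerant / counted | Proportion | Exact 95% CI |
|---|---|---|
| 0/10 (completers only) | 0% | 0% to 30.8% |
| 2/12 | 16.7% | 2.1% to 48.4% |
| 3/13 | 23.1% | 5.0% to 53.8% |
| 4/14 | 28.6% | 8.4% to 58.1% |

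**4. How often the missing rule would matter.** The chance of at least one intolerant person among 10 starters is 1 − (1 − p)^10. For assumed p of 5%, 10%, 20% and 30% it is 40%, 65%, 89% and 97%.

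**5. If 10 means starters.** With no replacement, losing 1, 2 or 3 people before the 60-minute test leaves 9, 8 or 7. Aim 1 power is then 0.75, 0.68 or 0.60. The two readings of 10 have different consequences, and the plan does not choose between them.

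**The case against.** The strongest reply is that tolerability is measured beyond the motor score. GSRS and adverse events are named as tolerability measures under Aim 2 itself, those who could not tolerate the regimen are phoned about side effects, and adverse events go to monthly investigator meetings. This stands as a description of data collection. It does not supply an outcome: no analysis, threshold or denominator is given for any of these measures. For those sent home, the stated purpose of the call is side effects, and the GSRS is not expressly required.

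A reader might go further and infer that the Aim 2 result comes only from people who tolerated the regimen. The documents do not say so. Being sent home without the supplement can be read as withholding the take-home KE supply, and someone with nausea or unfinished exercise could still be tested at 60 minutes.

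A reader might also infer that those sent home would be replaced. No replacement rule exists, and the Sample Size paragraph speaks simply of 10 participants, so the 2/12 to 4/14 illustrations depend on an assumption.

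Nor can it be said that the motor comparison is biased in favour of the regimen. People may stop for taste, stomach discomfort or muscle pain, and nothing shows that their motor change would be worse. The direction is unknown.

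Finally, the assumed rates may look high. The main protocol reports mild symptoms after 0.3% to 0.5% of 1,588 drinks, and mild nausea after 6 of 2,016 (0.3%). Those figures are per drink, for KE alone, in type 2 diabetes and healthy adults, so they do not settle the rate for supplement, KE and exercise together in fasted people with PD. The sub-study is also optional, single-day and sized for Aim 1, which limits the weight of the point but does not remove the mismatch.

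**Conclusion.** The point holds in this form: the only hypothesis, outcome and test for a tolerability aim is a motor score. That comparison may be limited to people who tolerated the regimen, and no stated outcome counts those who did not. This rests on the text alone.

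The size is not known, because it depends on an intolerance rate, departure times and a replacement practice that the documents do not give. Under the assumption of 2 intolerant among 12 starters, the difference is 17% (95% CI 2% to 48%) against 0 of 10. With samples this small the intervals are wide on either basis; the gain is a correct denominator, not precision. The change should be made before the sub-study is analysed.

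**What to change.** - Make the Aim 2 tolerability outcome the proportion of all participants who start the coffee/fat supplement who complete the supplement, KE and exercise, with an exact 95% CI.
- Report GSRS and side effects for all starters, including what is learned on the 48-hour call.
- Keep the MDS-UPDRS III change as a separate motor measure, and report with it the number of starters who lack a 1-hour score.
- State whether 10 means starters or completers, and keep any replaced participant in the denominator.

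The cost is mostly wording. Two small items are added: a record of the component at which a participant stopped and why, which is not in the Schedule of Activities, and the GSRS on the call to those sent home. The tolerability figure may be less favourable. No change to dosing or clinical management is implied.
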